15.3.2 Adverse Events Leading to Study Intervention Discontinuation

A listing of TEAEs leading to treatment discontinuation, interruption, or dose reduction of each study drug will be provided (one for M3258, additionally in part B: one for dexamethasone). This listing, sorted by regimen, dose level and subject ID, will include: dose level, subject ID, age, sex, type of myeloma, AE investigator term, SOC, PT, relationship to M3258 and dexamethasone (as applicable), seriousness, action taken with M3258 or dexamethasone (as applicable) (displayed as: Disc/IR/DR,)), start date (+treatment day), stop date (+treatment day), duration of AE, if treatment was stopped before start of AE: days since stop of treatment, and outcome.

15.4 Deaths, Other Serious Adverse Events, and Other Significant Adverse Events

15.4.1 Deaths

Not applicable for this iAP, are included in other listings

15.4.2 Serious Adverse Events

Not applicable for this iAP, are included in other listings.

15.5 Clinical Laboratory Evaluation

Laboratory values (including corresponding normal ranges) from the Lab will be used for patient profiles, an Edish plot, and line plots

CCI

CONFIDENTIAL
INFORMATION

22/38

M3258

First in Human Dose Escalation of M3258 as a Single Agent and Expansion Study of M3258 in Combination with Dexamethasone

MS201814-0010

Version 2.0

Laboratory results will be classified according to the latest NCI-CTC Version [at the moment 5.0]. Some of the toxicity gradings are based on laboratory measurements in conjunction with clinical findings. The classification will be derived from the laboratory results at a given assessment, thus ignoring additional clinical findings, except for the evaluation of blood glucose toxicity grade 1 and 2 the fasting state is required. Ignoring the fasting state might lead to overreporting of grade 1 and 2 events. Therefore, blood glucose grading will focus on grade 3 and 4 reporting only.

If it increases interpretability, graphical displays can be shown on a log-scale.

Line plots (with x-axis time, y-axis lab value), using different colors per regimen, dose level and different line types to identify participants, will be provided for the following lab parameters:

- Neutrophils
- Platelets
- Lymphocytes
- Hemoglobin

If available (and feasible due to potential differences between labs) reference lines for ULN and LLN should be added to the plots.

Hepatotoxicity assessment

A plot of peak ALT versus peak total bilirubin, both relative to the upper limit of normal (ULN) will be provided. This eDISH plot (evaluation of drug-induced serious hepatotoxicity) will have reference lines at $3 \times \text{ULN}$ for ALT and at $2 \times \text{ULN}$ for total bilirubin. Subjects outside the lower left box will be identified by subject-ID.

15.6 Vital Signs

Not applicable for this iAP, except for display of individual values in patient profiles

15.7 Other Safety or Tolerability Evaluations

Not applicable for this iAP, except for display of individual values in patient profiles

A listing of AEs of special interest will be provided. This will be sorted by regimen, dose level and subject. This listing will additionally contain age, sex, type of myeloma, SOC, PT, grade, SAE (yes/no), DLT per investigator (yes/no), relatedness to M3258 (yes/no), to dexamethasone (yes/no) (if applicable, in part B only), start date (+treatment day), stop date (+treatment day), duration of

CCI

CONFIDENTIAL
INFORMATION

23/38

M3258

First in Human Dose Escalation of M3258 as a Single Agent and Expansion
Study of M3258 in Combination with Dexamethasone

MS201814-0010

Version 2.0

Ac, action taken with M3258, if treatment was stopped before start of AE: days since stop of treatment, and outcome.

16 Analyses of Other Endpoints

16.1 Pharmacokinetics

PK concentration measurements will be descriptively summarized using: number of non-missing observations (N), arithmetic mean (Mean), standard deviation (SD), coefficient of variation (CV%), minimum (Min), median (Median) and maximum (Max). PK parameters will be summarized additionally, using the geometric mean (GeoMean), the geometric coefficient of variation (GeoCV) and the 95% confidence interval for the GeoMean (LCI 95% GM, UCI 95% GM). For time to reach maximum observed concentration (t_{max}), only n, Min, Median, and Max will be reported. PK parameters read directly from the measurements (i.e. C_{max}) will be reported with the same precision as the source data. All other PK parameters will be reported to 3 significant figures.

Descriptive statistics of PK concentration data will be calculated using values with the same precision as the source data and rounded for reporting purposes only. Descriptive statistics will only be calculated for $N > 2$ in which a measurement of <LLOQ represents a valid measurement.

Values below the lower limit of quantification of the assay (LLOQ) will be taken as zero for summary statistics of PK concentration data, PK parameter estimation (e.g. AUC) and for graphical presentations. It is expected that samples with concentrations above the upper limit of quantification (ULOQ) will be diluted and retested before the time of final analysis.

The following conventions will be applied when reporting descriptive statistics of PK data:

Mean, Min, Median, Max GeoMean, 95% CI: 3 significant digits

SD 4 significant digits

CV%, GeoCV%: 1 decimal place

The following PK parameters of M3258 and Dexamethasone (if applicable, in part B) will be calculated for both single and multiple dose, as applicable:

- C_{max} : Observed maximum plasma concentration
- $C_{max}/Dose$: Observed maximum plasma concentration, normalized by actual dose
- t_{max} : Time to reach maximum observed plasma concentration

CCI

CONFIDENTIAL
INFORMATION

24/38

M3258

First in Human Dose Escalation of M3258 as a Single Agent and Expansion
Study of M3258 in Combination with Dexamethasone

MS201814-0010

Version 2.0

- $AUC_{0-\infty}$: Area under the concentration-time curve from time zero extrapolated to infinity, based on the predicted value for the concentration at t_{last}
- AUC_{extra} : The AUC from time t_{last} extrapolated to infinity given as percentage of $AUC_{0-\infty}$. $AUC_{extra} = (\text{extrapolated area}/AUC_{0-\infty}) * 100$.
- AUC_{0-t} : Area under the concentration-time curve from time zero to the last sampling time at which the concentration is at or above the lower limit of quantification (LLOQ)
- AUC_{τ} : Area under the plasma concentration versus time curve within one dosing interval. $\tau = 24$ hours. For multiple dose the pre-dose concentration will be duplicated and used as the 24 hour concentration, to allow AUC_{τ} to be calculated (assuming steady state).
- AUC_{0-8} : Area under the plasma concentration versus time curve to 8 hours.
- $t_{1/2}$: Apparent terminal half-life
- λ_z : Apparent terminal rate constant
- CL/F : Apparent body clearance of drug following extravascular administration
- V_z/F : Volume of distribution of the drug following extravascular administration

Dose Normalized AUC ($AUC_{0-\infty}$, AUC_{0-t} , AUC_{τ} and AUC_{0-8}) will also be provided to enable comparisons between dose groups. Dose normalized AUC will be presented in a summary table.

For multiple dose the following will also be calculated, where possible:

C_{trough}	The concentration observed immediately before next dosing (corresponding to predose or trough concentration for multiple dosing)
$R_{acc}(AUC_{\tau})$	The accumulation factor to assess the increase in exposure until steady state is reached. $R_{acc}(AUC_{\tau}) = (AUC_{\tau} \text{ after multiple dose (at steady state)}) / (AUC_{\tau} \text{ after single dose})$
$R_{acc}(C_{max})$	The accumulation factor to assess the increase in maximum concentration until steady state is reached. $R_{acc}(C_{max}) = (C_{max} \text{ after multiple dose (at steady state)}) / (C_{max} \text{ after single dose})$
$R_{acc}(AUC_{0-\infty})$	The accumulation factor to assess the increase in exposure via $AUC_{0-\infty}$. $R_{acc}(AUC_{0-\infty}) = (AUC_{0-\infty} \text{ after multiple dose (at steady state)}) / (AUC_{0-\infty} \text{ after single dose})$

CCI

CONFIDENTIAL
INFORMATION

25/38

M3258

First in Human Dose Escalation of M3258 as a Single Agent and Expansion Study of M3258 in Combination with Dexamethasone

MS201814-0010

Version 2.0

CL _{ss/f}	The apparent total body clearance of study intervention at steady state following extravascular administration, taking into account the fraction of dose absorbed. CL _{ss/f} = Dose _{p.o.} / AUC _t
--------------------	--

Available individual M3258 and Dexamethasone (as applicable, in part B) plasma concentrations will be listed and summarized by regimen, dose, study day, analyte and scheduled collection time, including summary statistics where data allows. Individual as well as mean concentration-time profiles will be plotted on linear and log scales as follows:

- Spaghetti plots showing all individuals per regimen (where applicable) and dose group; Day 1 Cycle 1 and Day 15 Cycle 1.
- Individual per subject plots overlaying Cycle Day 1 and Cycle 1 Day 15 concentration profiles Mean concentration-time profile per Dose group with Cycle 1 Day 1 and Cycle 1 Day 15 overlaid (linear \pm SD, and semi-log)
- Mean concentration -time profiles per Day, overlaying Single and Multiple Dose (Day 1 and Day 15)

For M3258, PK parameters, as described above, will be calculated using commercial software (Phoenix® WinNonlin®). Available PK parameters will be listed and summarized by regimen, dose, study day and Analyte. Nominal collection times may be used for PK determinations in support of the SMC review.

The following plots will also be provided, for Key PK parameters:

- Dose Normalized C_{max} and AUC_t versus Dose level as a scatter plot with regression line. Plot axes will start at the origin (0,0), but the regression line should fit the data and not be forced through the origin.

PK listing creation and PK parameter calculation is outsourced to Covance by Merck Quantitative Pharmacology.

For the first 1-2 SMC meetings pre-clinical data/animal PK parameters may be presented in a table alongside observed human PK parameters in order to compare the ratios of AUC and C_{max}. This will be compiled by Merck Quantitative Pharmacology.

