Screening will be performed within 28 days prior to Day 1 of M3258 administration. The Screening period should start before the SMC decision to enroll participants to the next study intervention cohort. Treatment of the participants screened for future dosing cohorts will only start after the SMC decision to proceed to the next dosing cohort. If there are no clinically significant findings at Screening and the participant meets all the protocol-defined inclusion criteria and none of the exclusion criteria, the participant will be considered as eligible and will be enrolled into the study. Participants who fail to meet the protocol-specified criteria or who withdraw their consent will be considered Screening Failures.

Treatment Period

During dose escalation (Part A), M3258 will be administered QD as a single agent in 28-day cycles. In the expansion cohort (Part B), M3258 will be administered in combination with dexamethasone at a cumulative dose of 40mg/week. The treatment period will begin at the first dose of M3258 in Day 1 Cycle 1. Participants who tolerate M3258 without significant clinically relevant toxicities may continue to receive their assigned dose if there is no evidence of disease progression.

If QD treatment is not tolerated at a dose level showing efficacy and/or Pd marker signals, the following options will be considered by the SMC based on available data:

- QD dosing at doses below the non-tolerated dose (down to 1mg) in 28-day cycles (based on SMC recommendation)

OR

- Twice-per-week dosing on Days 1, 4, 8, 11, 15, 18, 22 and 25 in 28-day cycles

In addition, if a consistent reduction in platelet counts to thrombocytopenia \geq Grade 3 is observed during a 28-day dosing regimen without recovery to baseline or \leq Grade 2 by the end of the cycle, the SMC can consider a drug holiday of at least 7 days in the proposed regimen below. Similar to pan-proteasome inhibitors, a transient effect on megakaryocyte function, possibly related to platelet budding needs to be considered rather than a megakaryocyte cytotoxicity (Lonial et al, 2005). A predicted time for recovery of platelet counts from nadir to baseline values has been described to be around 7 days (Lonial et al, 2005). Thus, a drug holiday (intermittent) of at least 7 to 10 days is included in the proposed regimen below which consequently changes the cycle length to 21 days.

- QD dosing on Days 1 to 14, no dosing on Days 15 to 21, in 21-day cycles

OR

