- Twice-per-week dosing on Days 1, 4, 8, and 11, no dosing on Days 12 to 21, in 21-day cycles

If a switch in dose and/or regimen is recommended, the first tested dose level in the new regimen must not exceed the highest tested daily dose or the weekly cumulative dose must be equal to or lower than the highest weekly cumulative dose of regimen(s) tested so far.

The selected M3258 dose and regimen (RDE) will be combined with dexamethasone for the expansion cohort (Part B).

Dexamethasone will be given at a cumulative dose of 40 mg/week:

- 20 mg/day at Days 1, 4, 8, 11, 15, 18, 22 and 25 in a 28-day cycle

OR

- 20 mg/day at Days 1, 4, 8, 11, 15, and 18 in a 21-day cycle (regimen with drug holiday)

Dose Escalation Part A

Participants with MM whose disease has progressed following > 3 lines of therapy and for whom no effective standard therapy exists (see definition in Section 5) will be enrolled in the dose-escalation part of this study. The first dose escalation cohort will receive M3258 at the starting dose of 10 mg QD as a single agent. For further dose cohorts, a SMC will meet and review all available data to provide recommendations on the next dose level. The MTD is defined by the SMC with a target DLT rate of 25%. The following prespecified doses of 10

mg, 20 mg (100% increase), 35 mg (43% increase) and 50 mg (30% increase) are planned unless MTD is reached. The SMC, following review of preliminary safety, tolerability, PK and Pd information, will recommend the dose and/or the switch to an alternative regimen pre-specified in this protocol for the next cohort as applicable.

This may include proposing smaller dose increases compared to the prespecified doses and deescalation of the dose potentially down to 1mg.

The SMC may also recommend expanding a given cohort at the same dose level.

If additional dose levels above 50 mg are justified following review of preliminary safety, tolerability, PK, and Pd information from the initial cohorts, a protocol amendment will be submitted.

Depending on the observed toxicity profile, the SMC may decide on different doses as prespecified and/or change to regimens specified in this protocol. However, escalation may not proceed to any dose higher than 50 mg. In case escalation is recommended to proceed to doses higher than 50 mg, an amendment will be submitted. At each dose level, the first participant enrolled will be observed for DLTs for at least 48 hours before further participants are enrolled.

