Objectives	Endpoints (Outcome Measures)	Endpoints (Outcome Measures) Timeframe	IAP section
Primary	
To determine safety, tolerability and the maximum tolerated dose (MTD) (if observed) of M3258 as a single agent in participants with RRMM.
	
Occurrence of dose-limiting toxicities (DLTs) in participants receiving M3258 as a single agent during the first 28-day treatment cycle
 
Occurrence of any adverse events (AEs) reported (serious or nonserious) will be considered study treatment-emergent adverse events (TEAEs) and study treatment-related adverse events (TRAEs) (including TEAEs leading to death or discontinuation of treatment) in participants receiving M3258 as a single agent from start of study intervention to 30 days after end of study intervention
 
Occurrence of TEAEs outside of the DLT period that safety monitoring committee (SMC) deems relevant for determination of the MTD
 
Study treatment-emergent changes in clinical laboratory measures from Baseline, safety electrocardiogram (ECG) measures, vital signs, Eastern Co-operative Oncology Group (ECOG) performance status in participants receiving M3258 as a single agent from start of study intervention to 30 days after end of study intervention
	
For DLTs: from first treatment to 28 days after first treatment.
 
However, AEs occurring after the first 28 days that are considered relevant for dosing decisions can be defined as DLTs by the SMC.
 
For TEAEs and changes in lab values, ECG values, vital signs: from first day of study treatment (before treatment baseline measure) until 30 days after end of study intervention

Secondary	
To investigate the pharmacokinetic (PK) profile of M3258 (single and multiple dose exposure) in participants with RRMM
	
1. PK profile of M3258 in terms of C_{max}, AUC_{0-24}, AUC_{0-4} at Day 1 Cycle 1, (single dose); predose, 1, 2, 3, 4, 5, 6, 8 and 24 h after administration
 
2. PK profile of M3258 in terms of C_{max}, AUC_{0-24} at Day 15 Cycle 1, (multiple dose); predose, 1, 2, 3, 4, 5, 6, and 8 h after administration
	
Day 1: predose, 1,2,3,4,5, 6,8 and 24 h post dose
 
Day 15: predose, 1,2,3,4,5, 6,8 and 24 h post dose
 
AUC: predose to 24 h post dose on day 1 and day 15

CCI

CONFIDENTIAL INFORMATION

8/38

M3258

First in Human Dose Escalation of M3258 as a Single Agent and Expansion
Study of M3258 in Combination with Dexamethasone

MS201814-0010

Version 2.0

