$0 * P(\text{target dosing (estimated DLT rate in (0.2-0.35)}) + 1 * P(\text{under dosing (estimated DLT rate in [0-0.2])}) + 2 * P(\text{for over dosing (estimated DLT rate in (0.35-0.6])}) + 3 * P(\text{excessive dosing (estimated DLT rate in (0.60-1])})$.

The recommended dose level resulting from the model for the next cohort is the dose with the lowest loss function. This Bayesian escalation approach will be used to assist the SMC to select the next dose from a predicted set of acceptable doses, i.e., 10 mg, 20 mg, 35 mg, 50 mg. It is possible to choose a dose(s) not within the pre-specified dose-escalation plan. In this case the estimated posterior probabilities of the selected dose will also be provided to the SMC.

The model will continue to be updated at each SMC until the SMC has decided to stop dose escalation.

Prior distribution and likelihood are used to calculate the posterior probabilities based on Bayes theorem.

The likelihood is defined based on a binomial distribution, modelling the rate of subjects with at least 1 DLT.

The relationship between dose and toxicity rate is defined by

$$P(DLT|d_j, \alpha, \beta) = \frac{\exp\left(\alpha + \exp(\beta) * \log\left(\frac{d_j}{d_{ref}}\right)\right)}{1 + \exp\left(\alpha + \exp(\beta) * \log\left(\frac{d_j}{d_{ref}}\right)\right)}$$

Where $d_j \in \{10 \text{ mg, 20 mg, 35 mg, 50 mg}\}$ (or different) and (α, β) are bivariate normally distributed. Reference dose d_{ref} is 90 mg. The chosen prior for monotherapy escalation has the following parameters

$E(\alpha) = -0.708$,

$E(\beta) = -0.389$,

$SD(\alpha) = 1.2$, $SD(\beta) = 0.9$, $Cov(\alpha, \beta) = 0$.

The prior distribution has not been changed compared to the protocol defined.

CCI

CONFIDENTIAL
INFORMATION

18/38

M3258

First in Human Dose Escalation of M3258 as a Single Agent and Expansion
Study of M3258 in Combination with Dexamethasone

MS201814-0010

Version 2.0

Handling of changes in regimen

For different regimens, separate models will be used. In general, the same specifications outlined above will be used for each of these models, applicable to the dose given on the treatment days, unless otherwise specified. This means that in a once daily (QD) regimen, 90 mg as reference dose refers to the dosing of 90 mg daily. In a twice weekly regimen (on day 1,4,8,11, etc) the 90 mg reference dose refers to a dosing of 90 mg on day 1, day 4 etc. The approach is not considering weekly cumulative dosing.

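### The safety committee's PK plan reuses the predose value as the 24-hour concentration in every regimen; in twice-weekly dosing that sample is nominally 96 hours after the last dose, so AUC-tau and the figures built on it are not valid there

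*SAP*

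**What the plan says.** SMC IAP here means the plan in SAP Appendix 18.1; main IAP means the body of the SAP.

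- **Rule.** SMC IAP 16.1 defines AUC-tau as "Area under the plasma concentration versus time curve within one dosing interval", then fixes tau at 24 hours and adds, on the assumption of steady state: "For multiple dose the pre-dose concentration will be duplicated and used as the 24 hour concentration". Racc(AUC-tau), CLss/F, dose-normalized AUC-tau and a scatter plot of the last against dose are built on it.
- **Values below quantification.** The same section takes them as zero, including for AUC.
- **Regimens.** Protocol 4.1 allows "Twice-per-week dosing on Days 1, 4, 8, 11, 15, 18, 22 and 25 in 28-day cycles" and "Twice-per-week dosing on Days 1, 4, 8, and 11, no dosing on Days 12 to 21, in 21-day cycles". The modification history of SMC IAP version 2.0 gives the handling of different regimens as a reason for the revision, and section 15.1 adapts the DLT model: "In a twice weekly regimen (on day 1,4,8,11, etc) the 90 mg reference dose refers to a dosing of 90 mg". Section 16.1 summarizes PK by regimen, but the AUC-tau rule was left as it was.
- **Sampling.** Protocol Table 5 applies to all Part A regimens. After the Day 1 dose it has a 24-hour sample; after the Day 8 dose the last sample is at 8 hours. Day 15 has a predose sample only.
- **Internal conflict.** For the multiple-dose profile, the endpoint column of SMC IAP section 5 reads "at Day 15 Cycle 1, (multiple dose); predose, 1, 2, 3, 4, 5, 6, and 8 h after administration", while its timeframe column reads "Day 15: predose, 1,2,3,4,5, 6,8 and 24 h post dose".
- **Final analysis.** Main IAP 16.1.1 lists AUC0-8 and an accumulation ratio based on it. AUC-tau is not in its parameter table.

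**The concern.** A predose value can stand in for the 24-hour value only when the previous dose was given 24 hours earlier and successive intervals look alike. Twice-weekly dosing fails the first condition even at perfect steady state, because the previous dose is four days back. The numerator of Racc(AUC-tau) then ends on a sample about 96 hours old, while its denominator ends on a measured 24-hour sample. Daily dosing is hardly affected, so a comparison of daily with twice-weekly cohorts is distorted as well.

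The committee's dose recommendations draw on PK alongside safety and Pd data (Protocol 9.4.2 and 10). Protocol 2.2 asks the committee to bear in mind toxicity from accumulation over time, and Racc(AUC-tau) is one of the measures meant to show accumulation. Twice-weekly treatment was not hypothetical: main IAP 14.2 names 10 mg and 20 mg twice-weekly groups.

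**Working it through.** **Step 1. Age of the copied sample.** Hours since last dose = 24 × (PK day − previous dosing day).

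- Daily: 24 × (8 − 7) = 24 h. The plan's tau of 24 hours is reproduced.
- Twice weekly, Day 8: 24 × (8 − 4) = 96 h. It is not reproduced.
- Twice weekly, Day 15, 28-day cycle: 24 × (15 − 11) = 96 h. In the 21-day twice-weekly regimen Day 15 is not a dosing day.

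These are nominal times; the visit window is ±1 day.

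**Step 2. Model.** Half-life and LLOQ are not in the documents. Assumed: one compartment with oral absorption, ka 0.5 and 1.5 per hour, half-life 2 to 48 h, LLOQ of zero, 0.1% or 1% of Cmax. Doses fall at 0, 72 and 168 h. Samples are at predose and 1, 2, 3, 4, 5, 6 and 8 h after the Day 8 dose. AUC uses the linear-up, log-down rule of Protocol Appendix 8. Bias = AUC0-24 with the copied value ÷ AUC0-24 with the modelled 24-hour value − 1.

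**Step 3. Predose value quantifiable** (ranges span the two ka values).

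| Half-life | Bias in AUC-tau | True Racc | Racc under the rule |
|---|---|---|---|
| 12 h | −41.7% to −37.7% | 1.00 | 0.59 to 0.63 |
| 18 h | −39.3% to −36.2% | 1.03 | 0.63 to 0.66 |
| 24 h | −35.5% to −33.1% | 1.07 to 1.08 | 0.70 to 0.72 |
| 36 h | −29.0% to −27.4% | 1.21 to 1.22 | 0.87 |
| 48 h | −24.6% to −23.5% | 1.35 to 1.38 | 1.03 to 1.04 |

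Hand check at 12 h, ka 1.5, ignoring the small carry-over from earlier doses: k = ln 2 ÷ 12 = 0.0578.

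- AUC from 0 to 8 h, relative to the 8-hour value C8: [(1 − 0.630)/0.0578 − 1/1.5] ÷ 0.630 ≈ 9.1.
- True tail from 8 to 24 h: 16 × (1 − e^(−16k))/(16k) = 16 × 0.653 = 10.4.
- Tail with the copied value, which is about e^(−88k) = 0.0062 of C8: 16 × (1 − 0.0062)/5.08 = 3.1.
- Bias ≈ (3.1 − 10.4)/(9.1 + 10.4) = −37%, in line with −37.7%.

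CLss/F is dose divided by AUC-tau, so it moves the other way: 1/0.765 = 1.31 to 1/0.583 = 1.72, or 31% to 72% above the value that the modelled 24-hour concentration would give. A 24-hour area is in any case not the area over a 72- or 96-hour dosing interval, so that ratio is not a steady-state clearance in these cohorts.

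**Step 4. Predose value below quantification and set to zero.** The log rule cannot run to zero, so the last segment is linear.

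| Half-life | LLOQ, % of Cmax | Bias in AUC-tau | Racc under the rule (true 1.00) |
|---|---|---|---|
| 4 h | 0.1 or 1 | +13.2% to +15.8% | 1.13 to 1.16 |
| 6 h | 0.1 or 1 | +3.7% to +3.8% | 1.04 |
| 8 h | 0.1 or 1 | −4.7% to −3.5% | 0.95 to 0.97 |
| 12 h | 1 | −14.5% to −12.6% | 0.86 to 0.88 |

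The sign changes where the linear tail, 16 × C8/2, equals the true tail: (1 − e^(−x))/x = 0.5 with x = 16k, which gives x = 1.594 and a half-life of 16 × ln 2/1.594 = 7.0 h. At 2 h the result depends on whether the true 24-hour value is itself quantifiable: zero bias in three of the four cases and +25% in the other (ka 0.5, LLOQ 0.1%).

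At a 4-hour half-life the predose value is about one ten-millionth of Cmax, so the quantifiable case is not realistic there. At 12 h it is about 0.5% to 0.6% of Cmax.

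**Step 5. Daily dosing as control.** With a quantifiable 24-hour value the bias lies between 0% and −0.9% at every half-life tried.

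**The case against.** The strongest reply is that the rule was plainly meant for daily dosing. It presupposes steady state, the multiple-dose parameters are to be computed only as far as feasible, Protocol Appendix 8 defines tau as the dosing interval, and Protocol Table 7 restricts trough values to the daily regimen. That explains how the rule arose. It does not limit it: the number 24 is fixed, PK is reported by regimen, and the plan had just been revised for other regimens. The steady-state condition does not turn a 96-hour trough into a 24-hour concentration.

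A second reply is that the timeframe column of SMC IAP section 5 lists a 24-hour sample on Day 15, which would make copying unnecessary. The protocol schedules no such sample.

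The reply on consequence largely stands. The committee also receives Cmax, Racc(Cmax), AUC0-8, individual concentrations and profile plots, none of which depends on the copied AUC value. The dose-recommendation model uses DLT counts, not exposure, and the documents set no PK threshold for escalation. The main IAP uses AUC0-8. The study stopped for lack of enrollment before Part B (main IAP section 7), so a change cannot alter further dosing here.

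A reader might infer that exposure and accumulation were always understated, and hence that the error pushed toward escalation. The documents do not support this. The direction depends on half-life and LLOQ, which they do not give, and the zero rule reverses the sign at short half-lives. Nor do they show that any twice-weekly decision rested on AUC-tau.

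**Conclusion.** The rule is wrong as written for twice-weekly cohorts, whichever way the bias runs. AUC-tau, dose-normalized AUC-tau with its scatter plot, Racc(AUC-tau) and CLss/F are not valid there.

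The 96-hour gap follows from the dosing days alone. The size does not. It assumes one-compartment kinetics, ka of 0.5 to 1.5 per hour, and half-lives and an LLOQ that the documents leave open:

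- quantifiable predose value, half-life 12 to 48 h: about 23% to 42% too low, with Racc shown as 0.59 to 1.04 against 1.00 to 1.38;
- predose value set to zero: too high below a half-life of about 7 h, about 13% to 16% at 4 h, and too low above it;
- daily dosing with a quantifiable 24-hour value: at most about 1%.

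The defect is confined to these parameters in the committee's material and does not reach the final analysis.

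**What to change.** In SMC IAP 16.1:

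- limit the predose substitution to daily regimens;
- state tau separately for each regimen;
- for twice-weekly cohorts report AUC0-8 and Racc(AUC0-8), as the main IAP does, in place of AUC-tau, Racc(AUC-tau) and CLss/F.

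In SMC IAP section 5, reconcile the two columns on the 24-hour multiple-dose sample with Protocol Table 5.

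Because the SMC IAP is an appendix to the final plan, add a note that any twice-weekly AUC-tau, dose-normalized AUC-tau, Racc(AUC-tau) or CLss/F already given to the committee is not valid.

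The cost is a sentence or two of text and one programming condition. AUC0-8 needs no samples beyond those already scheduled in Part A.
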